8.1 Introduction: Study Design and Analysis Overview

The LTE is a longitudinal study of the long-term safety and effectiveness of PAH patients treated with AV-101 at different dose levels until being transitioned to the optimal dose of AV-101 which is selected after the completion of the Phase 2b Part of Study AV-101-002 (referred to as the parent study). About 370 subjects (with a maximum of 462 subjects) are expected to start the LTE. LTE subjects may be grouped into the following treatment groups:

- **Group 1 – Optimal Dose Treatment:** Subjects treated with the optimal dose throughout the parent trial and throughout their LTE participation.
- **Group 2 – Non-Optimal Dose Active Treatment, then Optimal Dose Treatment:** Subjects treated with active doses not selected as the optimal dose, who eventually will be treated with the optimal dose when this dose is selected.
- **Group 3 – Placebo to Non-Optimal Dose, then Optimal Dose Treatment:** Subjects originally assigned to the placebo arm during the parent trial then re-randomized to the two non-optimal active groups. Later, they will receive the optimal dose when it is selected.
- **Group 4 – Placebo to Optimal Dose Treatment:** Subjects originally assigned to the placebo arm during the parent trial then either re-randomized or switched to optimal dose.

Further characteristics of these LTE treatment groups are described in [Section 8.3](#).

Among the comparisons to consider are:

- 1) LTE levels and trends among subjects always on the optimal dose Group 1 will be compared in order with those of:
 - Group 4: Placebo to optimal dose treatment
 - Group 3: Placebo to non-optimal dose, then optimal dose treatment
 - Group 2: Non-optimal dose active treatment, then optimal dose treatment
- 2) Levels and trends in LTE safety and effectiveness endpoints for subjects always on the optimal dose (Group 1) will be compared to levels and trends during the parent study among these same subjects. This will be done to document whether the effects of the previous optimal dose on subsequent measures of effectiveness and safety while still undergoing treatment persist, improve, plateau, or dip the longer the duration of the optimal treatment.
- 3) Trends in continuous LTE effectiveness endpoints will be assessed separately for continuous dose intensity and continuous relative dose intensity.

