Trends or patterns over time in safety and effectiveness measures will be presented using repeated measures data analysis methods applicable to categorical or continuous data. Time-to-event analyses will be performed using Cox models with time-independent and time-varying covariates, specifically, extent of AV-101 dose intensity as continuous or categorical variables. For time to event data like overall survival, the starting period is the day prior to the first dose in the parent trial. Kaplan-Meier procedures for time -to-event analysis will also be performed.

For longitudinal continuous variables, the shape of the effectiveness trajectory (trends), repeated measures models over time will be fitted to assess whether the effectiveness measure indicates waxing, waning or remaining persistently over time. During the LTE, visits may be grouped into before or after optimal dose is administered. Levels of the LTE effectiveness endpoints before or after optimal dose treatment during the LTE will be reported.

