8.3 Treatment Exposure, Estimated Number of Subjects in Group Comparisons of Interest

LTE-eligible subjects from the Phase 2b and Phase 3 parts of the parent study will complete 24-weeks of treatment as part of that study, additional weeks of treatment under the same active treatment arms as they enter LTE and until they start optimal dosing once this dose is identified at the end of Phase 2b.

LTE-eligible subjects from the Phase 2b and Intermediate Parts of the parent study who are randomized to placebo will be re-randomized in a blinded manner to any of the active treatment dose groups at LTE entry and prior to being treated with the optimal dose at the end of Phase 2b. Depending on the timing of their enrollment and initial treatment in the Intermediate part of the study, treatment duration under the parent study will be at least 24 weeks prior to being treated

with the optimal dose at the end of Phase 3. The actual duration of treatment during the parent study, during the waiting period for the optimal dose and during the LTE, will be reported.

LTE subjects will be treated at different dose levels prior to the optimal dose being identified. In addition, duration of treatment under the parent dose among those in the Phase 2b and Intermediate Parts may vary before the optimal dose is identified at the end of Phase 2b. Thus time-varying treatment exposure is a key characteristic of the combined parent and LTE trials and will be considered in describing levels and trends in safety and effectiveness endpoints recorded during the LTE trial.

The actual number of subjects by LTE treatment groups will be reported. Summary descriptive statistics will be reported for dose intensity and relative dose intensity by LTE treatment groups. Patterns of continuous dose intensity will be described by fitting a polynomial regression with dose intensity as a response variable and weeks in the study as polynomial splines. In addition, levels and patterns of dose intensity (and relative dose intensity) over LTE time intervals will be described.

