Unstructured covariance will be specified. If the fitted model does not converge with unstructured covariance, a simpler covariance will be specified. LSMeans by trial treatment groups and difference in mean change from baseline in NT-proBNP at each visit will be reported. At each post-baseline visit (with focus on Weeks 24, 48 and 72 after LTE entry) the difference in mean change from baseline in NT-proBNP between treatment groups and its 95% CI for the treatment term will be reported. The mean difference in change from LTE baseline between subjects always on the optimal dose will be compared in the following order: 1) always on placebo (Group 4); 2) placebo followed by an active treatment dose (Group 3); 3) always on the non-optimal dose (Group 2). Average treatment effectiveness before and after optimal dose treatment during the LTE will also be presented.

Trends in change from baseline (CFB) will initially be assessed graphically. To obtain a measure of trends using MMRM, visits as continuous variables, and visit by LTE treatment groups interactions will be entered into the model. The coefficient for continuous visit associated for each of the LTE treatment groups indicates the linear trend in change from baseline over visit. A non-linear trend in CFB will be tested by entering visit as quadratic or cubic spline of visit in the model.

3) Maintenance or improvement in WHO Functional Class throughout the LTE

At each post-LTE baseline visit, a subject's status with respect to remaining in or decreasing from the same WHO FC will be recorded. At each post-baseline visit, the proportion of subjects who remain or improve on their baseline WHO FC will be reported by treatment groups. A logistic regression model will be fitted where the response at each visit is whether the subject remains in or improves in WHO FC. The explanatory variables consist of LTE treatment groups, visit, LTE treatment groups by visit, IPA/HPA or non-IPA/HPA category, and continuous LTE baseline REVEAL Lite 2.0 score.

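### In Groups 2 and 3 the Section 8.5.2 (2) trend model has no term for the move to the optimal dose, so a dose step can be read as waxing or waning

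*Combined protocol and SAP*

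**What the plan says.** Section 8.1 states the purpose for longitudinal continuous endpoints: "repeated measures models over time will be fitted to assess whether the effectiveness measure indicates waxing, waning or remaining persistently over time". Section 8.5.2 (2) turns this into a model: "To obtain a measure of trends using MMRM, visits as continuous variables, and visit by LTE treatment groups interactions will be entered into the model". Its group-specific visit coefficient is then taken as the linear trend ("The coefficient for continuous visit associated for each of the LTE treatment groups indicates the linear trend in change from baseline over visit"), and curvature is handled in the same variable: "A non-linear trend in CFB will be tested by entering visit as quadratic or cubic spline of visit in the model". The other listed terms are PAH category, baseline value and baseline REVEAL score. Neither current dose nor having moved to the optimal dose appears.

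Section 8.1 defines Group 2 as "Subjects treated with active doses not selected as the optimal dose, who eventually will be treated with the optimal dose when this dose is selected". Subjects in Group 3 go from placebo to a non-optimal dose: "Later, they will receive the optimal dose when it is selected". Section 8.3 adds that "duration of treatment under the parent dose among those in the Phase 2b and Intermediate Parts may vary before the optimal dose is identified".

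The plan does recognise the issue in general terms. Section 8.3 says: "Thus time-varying treatment exposure is a key characteristic of the combined parent and LTE trials and will be considered in describing levels and trends". The Synopsis, Section 8.1 and Section 8.5.2 (2) provide for levels or averages before and after optimal dosing. Section 8.1, comparison 3, plans trends by dose intensity. Comparison 4 plans levels and trends after 24 weeks of optimal dosing in all four groups. No model is specified for either set of trends.

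**The concern.** In Groups 2 and 3 the visit coefficient combines two things: change over time on a given dose, and the change of dose. Only the first answers the waxing, waning or persistence question. If the optimal dose does better on an endpoint, Groups 2 and 3 appear to improve with time; if it does worse, they appear to fade. Either can happen when the effect on each dose is constant. Any comparison of their trend with Group 1, which does not change dose, carries the same component.

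At stake is how a slope in Groups 2 and 3 is described. The primary safety objective is not involved.

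**Working it through.** The documents give no power, effect size, SD or group size for a trend test, so there is no planned figure to reproduce. The check asks what the specified coefficient estimates when the true slope is zero on both doses.

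**Inputs.** From Table 1: LTE 6MWT visits at Weeks 4, 12, 24 and every 12 weeks after, taken here to Week 72. From Section 8.5: two-sided 0.05. Assumed: residual SD 35 m, between-subject SD 40 m (it cancels from a within-subject slope), moves uniform over LTE Weeks 12-60, 40 or 80 subjects in the group, and steps of 5 or 10 m.

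**Step 1: slope produced by a pure step.** The seven visit weeks have mean 36.57 and Sxx = Σ(w − 36.57)² = 3757.7. For a unit step, slope = Sxd/Sxx, where Sxd sums (w − 36.57) over visits after the move. The fitted change from Week 4 to Week 72 is 68 × slope. For moves just after Weeks 12, 24, 36, 48 and 60 it is 1.03, 1.26, 1.27, 1.07 and 0.64 times the step.

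With moves spread over Weeks 12-60, Sxd averages (57.14 + 69.71 + 70.29 + 58.86)/4 = 64.0. The slope is 64.0/3757.7 = 0.01703 per week, or 0.204 of the step per 12 weeks. The fitted change is 68 × 0.01703 = 1.16 times the step.

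**Step 2: curvature does not help.** Under that spread the group mean at the seven visits is 0, 0, 0.25, 0.50, 0.75, 1, 1 times the step, which looks like gradual improvement. A quadratic in visit runs from −0.08 to 1.07 and a cubic from −0.01 to 1.01. A spline of visit is likewise a function of visit, not of each subject's move date.

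**Step 3: rejection of zero slope.** The SE of the mean slope per 12 weeks is 12 × 35/√(n × 3757.7): 1.083 m for n = 40 and 0.766 m for n = 80. The rejection probability is approximately Φ(z − 1.96) + Φ(−z − 1.96), with z = slope/SE.

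| Step | Share moving mid-LTE | Slope per 12 weeks | n = 40 | n = 80 |
|---|---|---|---|---|
| 10 m | all | 2.04 m | z = 1.89, 47% | z = 2.67, 76% |
| 10 m | half | 1.02 m | z = 0.94, 16% | z = 1.33, 27% |
| 5 m | all | 1.02 m | 16% | 27% |
| 5 m | half | 0.51 m | z = 0.47, 8% | z = 0.67, 10% |
| 0 | any | 0 | 5% | 5% |

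Simulation with t tests gives 45% and 76% for the first row and 15% and 26% for the second. The Group 1 versus Group 2 difference-in-slope test, for a 10 m step, rejects about 27-48% if all move and 10-17% if half do. A separate generalised least squares simulation in SD units (within-subject correlation 0.5, 50 subjects, all moving) rejects 54% for a 0.2 SD step.

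**Step 4: with a switch term.** Adding a subject-level post-move indicator brings the mean slope to about zero and rejection to about 4-7% in simulation, which is nominal within simulation error.

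**Step 5: cost in precision.** The slope SE is multiplied by 1/√(1 − R²), where R² = Sxd²/(Sxx × Sdd) and Sdd averages (10/7 + 12/7 + 12/7 + 10/7)/4 = 1.571. If all move, R² = 64.0²/(3757.7 × 1.571) = 0.69 and the factor is 1.81. If half move, R² = 32.0²/(3757.7 × 0.786) = 0.35 and the factor is 1.24.

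**The case against.** The strongest reply is that the plan does not ignore the move. It commits to before-and-after levels, dose-intensity trends, trends after 24 weeks of optimal dosing, and a general consideration of time-varying exposure. Section 8 is an overview that leaves detail to a SAP. This stands as far as it goes, and a reader who inferred that the plan is blind to the dose change would be wrong. But before-and-after averages are not slopes. The two trend commitments have no stated model. Section 8.1 computes average dose intensity as cumulative dose over treatment weeks, which blurs the move. None of this alters what the specified coefficient measures.

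Second, the formal tests are softer than a rejection rate suggests. Section 8.5.2 (2) calls the linear term a measure and promises a test only for non-linearity. Section 8.5 makes between-group trend tests optional and adjusts for multiplicity. That stands: the rates above show how often a dose step would look like a trend, not the error rate of a committed test.

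Third, not everyone moves mid-LTE. Under Section 3.1, Intermediate Part subjects entering after dose selection start on that dose. Under Section 5.5, down-titrated subjects may not be transitioned. That stands and is why the half-moving rows are shown.

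Fourth, a reader might infer that the Group 1 versus Group 2 or 3 contrasts at Weeks 24, 48 and 72 are also invalid. The documents do not support that. The groups are defined as treatment sequences, and comparing sequences at fixed LTE visits is legitimate. Nor do the LTE's persistence conclusions fail as a whole: Section 8.1, comparison 2, poses that question for Group 1, and the delayed-start analysis uses Groups 1 and 4.

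Finally, the Synopsis says efficacy measures are collected only for subjects on the open-label optimal dose. Read literally, there would be no pre-move values and no step to fit, though visits counted from LTE entry would still misstate time on the optimal dose. Table 1 and the before-and-after summaries in Section 8.5.2 (2) point the other way.

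**Conclusion.** The point holds for Groups 2 and 3 and for the trend model only. As specified, the visit coefficient is confounded with the change of dose, and no function of LTE visit alone can separate the two.

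The bias is proportional to the step and to the share of subjects moving mid-LTE, and it is zero if the move changes nothing. A reader might infer from the all-moving 10 m case that a false trend is likely. The documents supply neither the step nor the share, and a smaller step or fewer movers brings the rate down to about 8%. The existence of the bias is certain if there is a step; its size is not known. Groups 1 and 4 are exposed only through down titration.

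This should be corrected before any statement on waxing, waning or persistence is made for Groups 2 and 3.

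**What to change.** In the trend model of Section 8.5.2 (2), add a subject-level time-varying indicator for being on the optimal dose at each visit, with weeks since first optimal dose. Fitting pre-move and post-move visits separately would also serve. Report within-dose slopes for Groups 2 and 3. Base waxing, waning or persistence statements, and any trend comparison with Group 1, on those slopes. Use the same model for Section 8.1, comparison 4.

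Keep the by-visit contrasts at Weeks 24, 48 and 72, labelled as comparisons of treatment sequences. Correct the description of Group 2 in Section 8.5.2 (2), which reads as if those subjects never left the non-optimal dose, contrary to Section 8.1. Reconcile the Synopsis statement on when efficacy is collected with Table 1 and Section 8.5.2 (2).

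The change is to analysis wording. No new data are needed, because Section 8.6 already splits Groups 2 and 3 at the first day of optimal treatment, and Section 8.5.2 (4) already uses time-varying dose groups in its Cox model. The price is precision: under the assumptions above the slope SE grows by a factor of about 1.2 to 1.8 with the indicator alone, and separate slopes for each period may cost more.

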8.5.1 Delayed-Start Efficacy Analysis

The delayed-start analysis (Liu-Seifert et al., 2015; Wang et al., 2019) will be performed to evaluate potential disease modifying characteristics of the treatment. Week 24 and Week 48 data will be compared between Group 1 and Group 4. Group 1 (optimal dose treatment) is the early start group and Group 4 (placebo to optimal dose treatment) is the late start group. The analyses will include the following three comparisons:

- At Week 24, the change from baseline of an efficacy variable for Group 1 that achieves statistical significance compared with Group 4
- At Week 48, the change from baseline of an efficacy variable for Group 1 that achieves statistical significance compared with Group 4
- For the change from Week 24 to Week 48 of an efficacy variable, Group 1 is not inferior to Group 4

For continuous efficacy variables such as 6MWD, ANCOVA will be used with baseline 6MWD and randomization stratification factors as covariates. Normality will be examined using the Shapiro-Wilk test. If a normal distribution is rejected, a non-parametric Wilcoxon rank sum test stratified by stratification factors will be used. A multiple imputation method will be used to handle the missing data.

If Week 24 or Week 48 has missing data and subjects are still alive, a standard multiple imputation (MI) will be implemented using a regression model accounting for baseline 6MWD, randomization stratification factors, and if necessary, additional covariates such as demographic variables. For missing 6MWD data due to death, a random sample from the worst 10% change among all subjects will be used.

NT-proBNP is also a continuous variable; therefore, the delayed-start analysis will be performed similar to 6MWD.

The WHO function class improvement is a binary variable; therefore, the delayed-start analysis will be performed by Cochran-Mantel-Haenszel (CMH) test with randomization stratification factors as strata.

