8.5.2 Longer Term Analysis for the First Tier of Efficacy Endpoints

1) Overall survival throughout the parent trial and LTE study duration

Kaplan-Meier survival analysis will be performed. The probability of survival will be evaluated at one, three, and five (if there is sufficient follow-up time) years after initial study participation in the parent trial through the completion of the LTE trial.

A Cox regression analysis will be performed with baseline REVEAL Lite 2.0 category score and IPAH/HPAH or Non-IPAH/HPAH category. The hazard ratio and its 95% CI for the pairwise LTE treatment groups will be reported for Group 1 versus Group 4, Group 3, and Group 2 respectively.

2) Change from LTE baseline to post-LTE baseline in continuous effectiveness endpoints

The continuous endpoints measured at multiple timepoints include:

- Change from baseline in NT-proBNP
- Change from baseline in 6MWD
- Change from baseline in REVEAL Lite 2.0 Score
- Change from baseline in QoL emPHasis-10 Questionnaire score
- Change from baseline in Borg dyspnea index

The following analysis described for change from baseline in NT-proBNP will be used for the analysis of the continuous endpoints enumerated above.

The pairwise mean difference in change from LTE baseline among LTE treatment groups will be estimated using a mixed model for repeated measures (MMRM) model where the response is change from LTE baseline in an NT-proBNP at each post-baseline visit for each subject.

The explanatory variables will include:

- Fixed effect factors
 - Visit
 - LTE treatment groups
 - LTE treatment groups by visit interaction
 - IPAH/HPAH or Non-IPAH/HPAH category
- Fixed effect covariates
 - Continuous pre-LTE baseline value
 - Continuous parent trial baseline REVEAL 2.0 score
- Subjects as random effects

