Visits within a subject form a cluster. Estimated proportions by treatment group and visit will be reported. For Week 24 after optimal dose treatment, the log of odds and proportions of subjects who maintain or improve WHO FC and their 95%CI will be reported by treatment groups. Odd ratios (OR) and 95%CI for subjects always on optimal dose (Group 1) relative to those subjects on always on placebo (Group 4) will be reported. OR and 95%CI among subjects always on optimal dose (Group 1) relative to those of subjects on placebo and then active treatment (Group 3) and OR and 95%CI among subjects always on optimal dose (Group 1) relative to those of subjects on non-optimal dose (Group 2) will also be reported.

4) Time to Clinical Worsening

Time to clinical worsening while in the parent trial and LTE will be based on the first occurrence of any of the following events for each subject.

- Death
- Initiation of parenteral prostanoids
- Hospitalization for worsening PAH
- $\geq 15\%$ decline from baseline in 6MWD and accompanied with progression to or continued WHO FC III or IV symptoms

A subject is evaluated for experiencing any of the above components of clinical worsening throughout the parent trial and LTE study period. Time to clinical worsening is the number of days between the earliest occurrence of the clinical worsening component and the date of the first dose in the parent trial. With treatment groups that change over time intervals, event and censoring will be defined within each time interval. A subject who does not experience any of the clinical worsening component throughout a treatment period/interval is censored and is assigned time to worsening status by the end of the interval. Subjects who are lost to follow-up are typically considered censored. Supplemental analyses will be performed where subjects with an unknown clinical worsening event will be considered to

experience the event and the time to clinical worsening status is the last contact with the subject.

The probability of clinical worsening every 24 weeks after the first dose in the parent trial throughout the LTE will be reported, descriptively as well as based on a Cox model for time to clinical worsening while holding covariates at their means.

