A Cox model will be fitted to time to clinical worsening with terms for time-varying by treatment dose groups, continuous LTE baseline REVEAL Lite 2.0 score (among those randomized to placebo in Phase 3), continuous parent baseline REVEAL Lite 2.0 score, and IPAH/HPAH or Non-IPAH/HPAH category.

The hazard ratio and its 95% CI for the pairwise treatment dose groups will be reported for:

- Always on the optimal dose (Group 1) versus always on placebo (Group 4)
- Always on the optimal dose (Group 1) versus on placebo followed by an active dose (Group 3)
- Always on the optimal dose (Group 1) versus always on a non-optimal dose (Group 2)

Kaplan-Meier curves by parent trial treatment groups will be generated.

5) Achieving multicomponent clinical improvement will be analyzed as a binary as well as a time to event response throughout the LTE period

a) Binary response throughout LTE period: At each LTE visit, a subject response is set to 1 for achieving multicomponent clinical improvement if he meets all of the following three conditions:

- FC improvement or maintenance of FC II status
- NT-proBNP \geq 30% improvement or $<$ 300 pg/ml
- 6MWD \geq 30 meters improvement

Otherwise, the response value is 0.

A logistic regression model will be fitted to the binary response of achieving multicomponent clinical improvement at each visit. The explanatory variables will include LTE treatment groups categorical visit, LTE treatment groups by visit interaction, continuous LTE baseline REVEAL Lite 2.0 score, continuous parent baseline REVEAL Lite 2.0 score, and IPAH/HPAH or Non-IPAH/HPAH category. The subject's multicomponent clinical improvement status during the parent study may be considered as an explanatory variable. Subjects will be specified as clusters.

b) **Time to Event Response from start to end of the LTE:** Time to achieve multicomponent clinical improvement response is defined as the days since the first

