dose that a subject achieves clinical improvement in all 3 components from the start through the end of LTE. The number of days between the date that a subject meets all of the multicomponent improvement parameters and the first LTE dose date is the time to achieving multicomponent improvement. A subject who does not experience multicomponent improvement is censored during the time interval. A subject who is lost to follow-up without recording this multicomponent improvement is censored at the last visit in which the above parameters are recorded. Supplemental analyses will be performed where those lost to follow-up are considered a failure at the time of the lost to follow-up.

The Cox hazard model as described for time to clinical worsening will be implemented for time to multicomponent clinical improvement.

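### Section 8.5.2 gives no rule for death in the WHO FC response or the 6MWD and NT-proBNP MMRM, so the by-visit WHO FC results are conditional on survival

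*Combined protocol and SAP*

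**What the plan says.** **WHO FC, Section 8.5.2(3).** A subject's class relative to baseline is recorded at each visit, and then: "At each post-baseline visit, the proportion of subjects who remain or improve on their baseline WHO FC will be reported by treatment groups". A clustered logistic model uses the same visit-level response. The time point singled out for odds ratios is set by this text: "For Week 24 after optimal dose treatment, the log of odds and proportions of subjects who maintain or improve WHO FC". Neither a denominator nor a value after death is given.

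**Continuous endpoints, Section 8.5.2(2).** For the MMRM, "the response is change from LTE baseline in an NT-proBNP at each post-baseline visit for each subject", and the same model serves 6MWD. The text adds "Unstructured covariance will be specified" and a reporting emphasis "with focus on Weeks 24, 48 and 72 after LTE entry". It has no rule for missing values or death.

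**Clinical improvement, Section 8.5.2(5a).** The response is 1 if all three conditions are met at an LTE visit. "Otherwise, the response value is 0". Death is not named.

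**Delayed-start analysis, Section 8.5.1.** Multiple imputation is confined to subjects who are alive, and: "For missing 6MWD data due to death, a random sample from the worst 10% change among all subjects will be used". NT-proBNP is to be analysed in the same way. The WHO FC test in that section has no death rule.

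**Related text.** Section 6.8.2 treats death as withdrawal from the study. The Full Analysis Set in Section 8.2 requires at least one effectiveness measure after LTE entry. The opening of Section 8 leaves further detail to a separate SAP.

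**The concern.** A subject who has died has no visit and no recorded class, so an analyst who follows 8.5.2(3) literally has nothing to enter. The subject leaves numerator and denominator together. A death before any post-entry measure removes the subject from the Full Analysis Set altogether, unless death itself is read as such a measure. Yet nobody would call a subject who died someone who maintained functional class.

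The MMRM raises a different problem. It does not describe survivors. Under missing at random it carries each deceased subject forward along the path predicted from earlier visits. For 6MWD and NT-proBNP, 8.5.1 gives a death at Week 48 an unfavourable value, while 8.5.2 implicitly gives the same death a living subject's expected value.

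At stake are the reported level of functional class over time and the comparisons of Group 1 with Groups 4, 3 and 2.

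**Working it through.** The plan gives no event rate, effect size or power for these analyses, so there is no figure of its own to reproduce. What follows is illustration.

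**Inputs**
- Registry survival from Section 1.1: 85% at 1 year, 68% at 3 years and 49% at 7 years, counted from diagnostic right heart catheterization.
- Assumed: constant hazard, clock started at LTE entry, 52.18 weeks per year.
- Assumed: proportion m of survivors maintaining or improving class, 0.75 for the level and 0.7 to 0.9 for group comparisons.
- Assumed: hazard ratio (HR) between two groups of 1.5 to 3.

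**Step 1: deaths.** The hazard is λ = −ln S(T)/T, which gives 0.1625 per year from the 1-year figure, 0.1286 from the 3-year figure and 0.1019 from the 7-year figure. Deaths by week w are 1 − exp(−λw/52.18).

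| Hazard from | Week 24 | Week 48 | Week 72 |
|---|---|---|---|
| 1-year survival | 7.2% | 13.9% | 20.1% |
| 3-year survival | 5.7% | 11.2% | 16.3% |
| 7-year survival | 4.6% | 9.0% | 13.1% |

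A piecewise hazard through the 1- and 3-year figures, conditional on surviving the 24-week parent study, gives 7.2%, 12.2% and 16.6%. These values lie within the table's range.

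**Step 2: level of the WHO FC proportion.** With death as failure the proportion is m × S(w), which is below m whenever anyone has died. With m = 0.75:
- Week 24: 0.75 × 0.928 = 69.6% to 0.75 × 0.954 = 71.6%.
- Week 72: 0.75 × 0.799 = 59.9% to 0.75 × 0.869 = 65.2%.

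Among survivors the figure is 75% at both visits.

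**Step 3: comparison of two groups.** Take equal m, the 3-year hazard in the reference group and S_B = S_ref^HR in the other. The difference that a survivor-only analysis cannot show is m × (S_ref − S_B). With m = 0.80 and HR = 2, survivors give 80% v 80% and an odds ratio of 1.00. With death as failure:
- Week 24: 75.4% v 71.1%, odds ratio (0.711/0.289)/(0.754/0.246) = 0.80.
- Week 72: 67.0% v 56.1%, odds ratio 0.63.

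Over m from 0.7 to 0.9 and HR from 1.5 to 3, the hidden difference is 1.9 to 9.5 points at Week 24 and 5.0 to 22.5 points at Week 72. At HR = 1 it is zero.

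**Step 4: MMRM.** A simulation used 400,000 subjects per group and three visits. An assumed frailty worsened the outcome and raised the chance of death. The mean change would be 0 m in both groups if nobody died. Results at the third visit (Week 72):

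| | Fewer deaths (15.6%) | More deaths (28.1%) |
|---|---|---|
| Mean in survivors | +7.8 m | +13.4 m |
| MMRM-type estimate | +4.7 m | +8.4 m |
| Deaths given the worst-10% mean | −7.7 m | −13.7 m |

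The MMRM-type estimate lies between zero and the survivor mean and favours the group with more deaths. The worst-10% rule reverses the order. The simulation had no baseline covariate and took the worst tenth within each group, where 8.5.1 takes it across all subjects. Only the direction should be read from it.

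**The case against.** The strongest reply is that silence is not a statement. A reader might infer that the plan treats deaths as missing and removes them from the denominator, but no section says so, and a separate SAP may settle it. That limits the claim to what follows when the text is applied as written. It does not supply a rule.

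A reader might also extend the point to clinical improvement. The documents do not support that: item 5(a) already has a default of 0, and a subject who has died does not meet the three conditions. The only doubt is whether the default reaches visits that never took place.

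Nor do the two efficacy sections conflict on WHO FC, since 8.5.1 has no death rule for its own WHO FC test. The contrast holds for 6MWD and, by extension, NT-proBNP, and 8.5.1 covers only Groups 1 and 4 at Weeks 24 and 48.

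On timing, the Week 24, 48 and 72 emphasis belongs to the MMRM. The WHO FC odds ratios are singled out at Week 24 after optimal dose, so the Week 72 figures bear only on the by-visit proportions. LTE Week 24 is itself a stand-in for subjects who switch dose later.

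On size, registry survival runs from diagnosis. LTE entrants have completed 24 weeks and have been judged suitable, so they may do better. All groups receive AV-101 and are to move to one dose, so mortality may be similar across groups.

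Finally, deaths are not hidden: they count in overall survival, time to clinical worsening and the fatal adverse event tables. That is correct, but none of those outputs changes the WHO FC odds ratios. A result conditional on survival can be a legitimate choice, but the plan does not say that it is making one.

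**Conclusion.** The point stands in limited form. As written, 8.5.2(3) yields WHO FC proportions and odds ratios conditional on being alive. The inflation of the absolute proportion needs only that some subjects die: about 3 to 5 points at Week 24 and 10 to 15 points at Week 72 under registry-type mortality and 75% maintenance among survivors. Distortion between groups also needs unequal mortality.

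For 6MWD and NT-proBNP, the MMRM implicitly estimates a mean as if nobody died. It favours the group with more deaths only if mortality differs and the frailer subjects are the ones who die.

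It would be too strong to say that these analyses as a whole describe survivors at Weeks 24 to 72, or that they necessarily flatter one group. The sizes rest on assumed inputs and are not forecasts for this trial.

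**What to change.** 1. In 8.5.2(3), set the response to 0 (not maintained) at every scheduled visit after death. Keep LTE-treated subjects who die before any post-entry measure in the denominator.
2. In 8.5.2(5a), confirm that the default of 0 covers visits scheduled after death.
3. For 6MWD and NT-proBNP in 8.5.2(2), add one sensitivity analysis that applies the worst-10% rule of 8.5.1 to post-death visits.
4. Show the number dead by group and visit beside each of these results.

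The cost is a few sentences in the SAP and one extra run, with no new data. The proportions will look slightly less favourable. The rule should be written before results by dose group are seen, so that the choice cannot appear driven by them.
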